5.3 Exploratory/ Additional Endpoints

TAK-653-1001 Statistical Analysis Plan Final Page 14 of 32 22 August 2017

6.0 DETERMINATION OF SAMPLE SIZE

The sample size chosen of 8 subjects in each Cohort (6 active: 2 placebo) is considered to be sufficient for evaluation of safety, tolerability, and PK of each cohort. The sample size was not based on statistical power considerations.

7.0 METHODS OF ANALYSIS AND PRESENTATION

7.1 General Principles

All study-related raw and derived data will be presented in data listings as appropriate. Continuous data will be summarized using number of subjects (N), mean, standard deviation (SD), median, minimum, and maximum, where appropriate. Where indicated, coefficient of variation (%CV) and geometric mean will also be included in the summary of continuous data. Categorical data will be summarized using the number and percentage of subjects for each category where appropriate.

All statistical tests will be 2-tailed at α =0.05 level for significance unless otherwise stated. The p-values less than or equal to α (when rounded to 3 digits) are reported as "significant". The phrase "no significant difference" indicates that all p-values for the tests are greater than α . All computations will be performed prior to rounding.

Subjects who take placebo in each cohort group will be pooled together in all safety summaries for each part (Part 1 and Part 2) and will be analyzed as one placebo group.

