Additionally, box plots of TAK-653 dose-normalized C_{max} and AUCs versus dose will be provided for each part (fasted cohorts only). Box plots of TAK-653 C_{max} and AUCs comparing fasted versus fed cohorts will also be provided.

Dose proportionality will be tested for SRD cohorts (fasted cohorts only) on Day 1 and for SRD/MRD cohorts after multiple dosing on Day 18 for TAK-653 C_{max} and AUCs using a power model. The power fit will be assumed as described by the following equation:

 $\ln(PK \ Parameter) = \beta_0 + \beta_1 \ln(Dose) + \varepsilon$

where β_0 is the intercept and β_1 is the slope. The dose proportionality will be declared when the 90% confidence interval for β_1 lies entirely within the critical region.

$$\left(1 + \frac{\ln(0.80)}{\ln(r)}, 1 + \frac{\ln(1.25)}{\ln(r)}\right)$$

where r is the ratio of the highest and the lowest dose in this study. This criterion implies that the 90% CI for the ratio of the central values of PK parameter of interest from the highest dose to the lowest dose is contained completely within the bioequivalence range of (0.80, 1.25) [2]. Plots of ln(AUC) or ln(C_{max}) vs ln(Dose) may also be used to illustrate dose proportionality or lack of it.

A power model will be performed to test whether the slope=1 in the power model and whether the point estimate of the slope is significantly different from 0 or not.

The effect of food on the PK of TAK-653 will be evaluated via a paired t-test. The point estimates and 90% CIs for the ratio of C_{max} and AUC central values for TAK-653 tablets administered after fed conditions vs those obtained in the fasted state will be determined. The food effect on t_{max} will also be evaluated using a non-parametric Wilcoxon rank sum test.

All attempts will be made to have a distribution of ^{CCI} times within the prescribed window of 2 to 6 hours postdose on Day 12 for SRD/MRD Cohort 3; for example, the ^{CCI} may be collected at 2 hours postdose from the first subject, 3 hours postdose from the

| TAK-653-1001 | Page 22 of 32 |
|---------------------------------|----------------|
| Statistical Analysis Plan Final | 22 August 2017 |
| | |

second subject, 4 hours postdose from the third subject, and 6 hours postdose from the fourth subject with a collection window of +1 hour for each subject.

| The CCI | , if available, will be presented |
|--|---------------------------------------|
| in a data listing. The ratio of TAK-653 ^{COI} | on Day 12 to the TAK-653 plasma |

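### SAP 7.1 sets tests at a two-tailed 0.05 level but applies the cut-off after rounding the p-value, so the rule as written works at 0.0505 for a continuous test: a small internal inconsistency

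*SAP*

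**What the plan says.** One paragraph of SAP 7.1 holds four statements that bear on significance.

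1. The level: "All statistical tests will be 2-tailed at α =0.05 level for significance unless otherwise stated".
2. The label for a positive result: "The p-values less than or equal to α (when rounded to 3 digits) are reported as 'significant".
3. The label for a negative result: "The phrase 'no significant difference' indicates that all p-values for the tests are greater than α". Rounding is not mentioned here.
4. The order of calculation: "All computations will be performed prior to rounding".

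The tests that the paragraph can reach are in SAP 7.7.2. For the power model: "A power model will be performed to test whether the slope=1 in the power model", together with a test of the slope against 0. For food: "The effect of food on the PK of TAK-653 will be evaluated via a paired t-test". For time to peak: "The food effect on t_{max} will also be evaluated using a non-parametric Wilcoxon rank sum test". Dose proportionality itself is settled by an interval, not by a p-value: "The dose proportionality will be declared when the 90% confidence interval for β_1 lies entirely within the critical region".

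**The concern.** A level and a decision rule stated next to each other should give the same answer for every p-value, and here they do not. Take p = 0.0504. It exceeds 0.05, so it is not significant at the level in statement 1. Rounded to three decimals it is 0.050, which is not above alpha, so statement 2 calls it significant. If statement 3 defines its phrase, the same value also qualifies as showing no significant difference.

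An SAP exists to fix such rules before results are seen. As written, a borderline food-effect or slope result could be reported either way, with support from the text for both.

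**Working it through.** **Inputs.** Alpha = 0.05, two-tailed, and the round-then-compare rule (SAP 7.1). Six active subjects in SRD Cohort 3, the food-effect cohort (SAP 4.4), so 5 df for the paired t-test if all six complete both periods. Six SRD dose levels and five SRD/MRD dose levels in the SAP 4.4 tables, so 6 × 6 − 2 = 34 df and 5 × 6 − 2 = 28 df for the slope tests if every active subject contributes.

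**Step 1: the plan's own figure.** Comparing the unrounded p-value with 0.05 gives a size of exactly 0.0500 for a continuous test, because p is uniform under the null. The rule therefore reproduces the stated level only when nothing is rounded.

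**Step 2: the rule as written.**

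| Unrounded p | To 3 decimals | Label, rounded rule | p ≤ 0.05 unrounded? |
|---|---|---|---|
| 0.0499 | 0.050 | significant | yes |
| 0.0500 | 0.050 | significant | yes |
| 0.0501 | 0.050 | significant | no |
| 0.0504 | 0.050 | significant | no |
| 0.05049 | 0.050 | significant | no |
| 0.0505 | 0.051 (half-up) | not significant | no |

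The cut-off is 0.0505. The excess is 0.0505 − 0.0500 = 0.0005, and 0.0505 / 0.0500 = 1.01, or 1% in relative terms. Half-even rounding would also admit 0.0505 itself, which does not change the size of a continuous test.

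**Step 3: the other reading of three digits.** With three significant digits, 0.05004 becomes 0.0500 and passes, while 0.05005 becomes 0.0501 and fails. The cut-off is 0.05005 and the excess is 0.00005, one tenth of the excess in step 2.

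**Step 4: critical values at 0.05 and at 0.0505, two-tailed.**

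| Reference distribution | At 0.05 | At 0.0505 |
|---|---|---|
| Normal | 1.9600 | 1.9557 |
| t, 5 df (food effect) | 2.5706 | 2.5624 |
| t, 28 df (SRD/MRD slope) | 2.0484 | 2.0436 |
| t, 34 df (SRD slope) | 2.0322 | 2.0276 |

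For example, a paired t of 2.564 on 5 df gives p = 0.0504. It is labelled significant although it falls short of 2.5706.

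**Step 5: simulation.** In 4 million null paired t-tests with n = 6, the rejection rate was 0.04986 on unrounded and 0.05034 on rounded p-values. The share in the disputed band was 0.00048. The standard error of the first rate is √(0.05 × 0.95 / 4,000,000) ≈ 0.0001, so these results fit 0.0500, 0.0505 and 0.0005.

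**Step 6: which analyses can be touched.**

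- Food-effect paired t-tests on peak concentration and AUC: yes.
- Power-model tests of slope = 1 and slope = 0: yes.
- Food effect on time to peak: no, with exact p-values and no ties. For a rank sum test of 6 against 6, the attainable two-sided values on either side of 0.05 are 0.0411 and 0.0649. For a signed-rank test with n = 6 they are 0.03125 and 0.0625. None lies in the band.
- Dose-proportionality declaration: no, since it uses a 90% confidence interval.
- Laboratory, vital-sign and ECG data: no, since SAP 7.9.2 to 7.9.4 specify no tests. The other safety summaries (SAP 7.9.1, 7.9.5, 7.9.6) are counts, percentages and listings.

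**The case against.** The best defence is that the SAP gives one operational rule (round, then compare) and discloses it in advance. A programmer would obtain a single answer for p = 0.0504. Statement 3, read strictly, runs one way only: wherever the negative phrase is used, all p-values exceed alpha. That always holds, because any p that fails the rounded rule is above 0.05. Statement 4 is also compatible: the p-value is computed from unrounded inputs and rounded afterwards.

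Much of this stands. The clash with statement 3 arises only if that sentence is read as a definition, which is its natural reading but not the only one. Statement 4 is not a contradiction. It is not a cure either, because the parenthesis in statement 2 expressly places the comparison after rounding. What the defence does not remove is the gap between statements 1 and 2: a rule that rejects at 0.0505 is not a test at 0.05, and disclosing it does not make the two figures equal.

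A reader might infer more than the documents support:

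- *That significance labels will disagree with reported confidence intervals.* A label at p = 0.0504 would disagree with a 95% interval, but the visible SAP plans 90% intervals for the food effect and the slope. Any two-sided paired-t p-value below 0.10 already gives a 90% interval for the fed/fasted ratio that excludes 1.
- *That every p-value or conclusion is exposed.* The sentence is general in form, but step 6 of the check leaves two families of tests, and no stated decision rule in the visible text depends on either.
- *That the SAP contains a calculation error.* No figure in it is miscalculated; the fault lies in how the sentences fit together.

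**Conclusion.** The inconsistency is real and very small. On the three-decimal reading, and for a continuous test, the rule in SAP 7.1 has an effective two-tailed level of 0.0505 against the stated 0.05. About 0.0005 of null results per test would change label. On the significant-digits reading the level is 0.05005.

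Only a borderline food-effect paired t-test or power-model slope test could be mislabelled. No safety summary and no dose-proportionality declaration depends on it, and the sample size was not based on power (SAP 6.0).

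The conclusion rests on these assumptions: three digits means three decimals; p is uniform under the null for the t-based tests; all six active subjects of SRD Cohort 3 complete both periods; and the Wilcoxon p-values are exact and free of ties. It covers visible text only. Part of the pharmacodynamic section (SAP 7.7.6) is blacked out, so tests there cannot be judged.

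**What to change.** Replace the sentence in SAP 7.1 with: *Unrounded p-values less than or equal to alpha are reported as significant; p-values are rounded to 3 decimal places for display only.* This restores a level of exactly 0.05 for a continuous test, agrees with the sentence that follows on either reading, and settles what three digits means.

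The cost is one sentence of SAP text and a check that the programs compare the stored p-value, not the formatted one. No data, analysis or sample size changes. One side effect is that a p-value of 0.0504 would print as 0.050 without being called significant. A table footnote, or a fourth decimal for values in that narrow band, would prevent confusion.

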7.1.1 Missing Data

There will be no imputation of incomplete or missing data. Decisions regarding inclusion or exclusion of data from an analysis for subjects who are noncompliant with the dose schedule, or who have incomplete data, will be made on a case-by-case basis, but the data will be presented in data listings regardless.

Plasma concentrations that are below the limit of quantification (BLQ) will be treated as zero for summarizing concentration values and deriving PK parameters. These values will be flagged in the data listings, and deviations from this convention may be considered on a case-by-case basis as deemed appropriate.

7.1.2 Derived Datasets and Variables

Derived datasets will be generated according to CDISC guidance documents: Analysis Data Model (ADaM) Implementation Guide, Version 1.0 (17 Dec 2009); ADaM Data Structure for Adverse Event Analysis, Version 1.0 (10 May 2012).

7.1.3 Definition of Study Days and Baseline

For all safety endpoints, Baseline is defined as the last non-missing measurement prior to first dose of study drug for Part 1 SRD Cohorts and Part 2 SRD/MRD Cohorts. Baseline is defined as the last non-missing measurement prior to the first dose of study drug in each period (fed and fasted) for Part 1 Food Effect Cohort. Study day will be calculated relative to the date of the first dose in the study. Study day prior to the first dose of treatment will be calculated as: date of assessment/event – date of treatment; study day on or after the date of first dose of treatment will be calculated as: date of assessment/event – date of treatment + 1.

| TAK-653-1001 | Page 17 of 32 |
|---------------------------------|----------------|
| Statistical Analysis Plan Final | 22 August 2017 |

| 7.2 | Analysis Sets | |
|--------|------------------|---|
| Safety | ⁷ Set | The safety set will consist of all subjects who are enrolled and received 1 dose of study drug. Subjects in this analysis set will be used for demographic, other baseline characteristic, and safety summaries. |
| Rando | omized Set | The randomized set will consist of all subjects who are enrolled and randomized. |
| PK Se | et | The PK set will consist of all subjects who receive study drug and have at least 1 measurable plasma concentration or amount of drug in the urine. |
| PD Se | t | The PD set will consist of all subjects who receive study drug and have at least 1 postdose PD measurement. |

If any subjects are found to be noncompliant in dosing schedule or to have incomplete data, a decision will be made on a case-by-case basis as to their inclusion in the analysis but data for these subjects will be presented in the data listings.

7.3 Disposition of Subjects

Number of subjects randomized by site will be summarized separately by pooled placebo, each TAK-653 dose level, pooled TAK-653, and overall total for each part.

The number and percentage of subjects, who are randomized but not treated, complete study drug, prematurely discontinue study drug and study visits will be summarized by pooled placebo, each TAK-653 dose level, pooled TAK-653, and overall total for each part for subjects in the Randomized Set. In addition, the number and percentage of subjects will be summarized for each reason of discontinuation of study drug and study visits by pooled placebo, each TAK-653 dose level, pooled TAK-653, and overall total for each part. Subjects' study completion data, including reasons for premature termination, will be listed by dose level for all subjects.

The number and percentage of subjects who comprised each analysis set will be summarized by pooled placebo, each TAK-653 dose level, pooled TAK-653, and overall total for each part.

7.4 Demographic and Other Baseline Characteristics

Demographic and other baseline characteristics (caffeine consumption, smoking status, and female reproductive status) will be summarized by pooled placebo, each TAK-653 dose level, pooled TAK-653, and overall total for each part, and by overall total for combined Part 1 and Part 2. Summary statistics (N, mean, SD, median, minimum, and maximum) will be generated for continuous variables (eg, age, height, weight and BMI), and the number and percentage of subjects within each category will be presented for categorical variables (eg, gender, race, and ethnicity).

| TAK-653-1001 | Page 18 of 32 |
|---------------------------------|----------------|
| Statistical Analysis Plan Final | 22 August 2017 |

For each part, demographic variables of screen failure subjects and reasons for screen failure will be summarized for all subjects who are screened but not enrolled in the study. Individual demographic characteristics, date of informed consent, any available safety data, and reason for screen failure will also be presented in the data listing.

7.5 Study Drug Exposure and Compliance

The date and time of each dose for each subject will be reported in the data listing for all subjects. Summaries of PK plasma concentration and exposure data will be provided by TAK-653 dose level as well as listed in data listings. No other summary statistics for the extent of exposure to study drug or compliance calculations will be performed for this study.

7.6 Efficacy Analysis

Not applicable.

7.7 Pharmacokinetic/Pharmacodynamic Analysis

7.7.1 Plasma Pharmacokinetic Concentrations

Collection of Blood Samples for PK Analysis (All SRD Cohorts)

| Sample Type | Dosing Day | Scheduled Time (hours) |
|-------------|------------|---|
| Plasma | 1 | Predose (within 15 minutes prior to dosing) and at 0.25, 0.5, 1, 1.5, 2, 3, 4, 6, 8, 10, 12, 16, 24, 36, 48, 72, 96, 120 and 144 hours postdose. Additional collection at 168 hours postdose for Cohort 6 onward. |

Collection of Blood Samples for PK Analysis (All SRD/MRD Cohorts)

| Sample | | |
|--------|------------|---|
| Туре | Dosing Day | Scheduled Time (hours) |
| Plasma | 1 | Predose (within 15 minutes prior to dosing) and at 0.25, 0.5, 1, 1.5, 2, 3, 4, 6, 8, 10, 12, 16, 24, 36, 48, 72, 96 and 120 (a) hours postdose. |
| Plasma | 6 | 0.5, 1, 2, 4, 6, 8, 12, 16, and 24 (b) hours postdose. |
| Plasma | 12, 14, 16 | Predose (within 15 minutes prior to dosing) (and following ^{CCI} collection procedure on Day 12 (SRD/MRD Cohort 3 only). |
| Plasma | 18 | Predose (within 15 minutes prior to dosing) and at 0.25, 0.5, 1, 1.5, 2, 3, 4, 6, 8, 10, 12, 16, and 24 hours postdose. |

(a) The 120-hour sample must be collected before dosing on Day 6.

(b) The 24-hour sample must be collected before dosing on Day 7.

For each part, the concentration of TAK-653, ^{CCI} in plasma will be summarized by TAK-653 dose level, Day, and period (fasted vs fed) over each scheduled sampling time using descriptive statistics (N, arithmetic mean, SD, median, minimum, and maximum). Individual plasma concentration data versus time will be presented in a data listing.

| TAK-653-1001 | Page 19 of 32 |
|---------------------------------|----------------|
| Statistical Analysis Plan Final | 22 August 2017 |

Blood samples for placebo will not be analyzed by the bioanalytical laboratory except for 2 samples per subject receiving placebo, 1 predose and the other around the expected time at which C_{max} occurred (as emerging from the actual measurement of the samples of the first dose group) to ensure from a safety perspective that no additional subjects were on active treatment. These data will be listed but not summarized.

For each part, individual concentrations of TAK-653, ^{CCI} in plasma will be plotted by actual time on linear and semilogarithmic scales. Plots of mean TAK-653, ^{CCI} plasma concentrations versus nominal time will also be provided on linear and semilogarithmic scales.

7.7.2 Plasma Pharmacokinetic Parameters

The PK parameters of plasma TAK-653 and its metabolites ^{CCI} will be determined from the concentration-time profiles for all evaluable subjects. Actual sampling times, rather than scheduled sampling times, will be used in all computations involving sampling times. The following PK parameters will be calculated using non-compartmental analysis using Phoenix WinNonLin version 6.4 or higher.

| Symbol/Term | Definition |
|---|---|
| AUC ₂₄ | Area under the plasma concentration-time curve from the time 0 to time 24 hours postdose. |
| AUC_{τ} | Area under the plasma concentration-time curve during a dosing interval |
| AUC _{last} | Area under the plasma concentration-time curve from time 0 to time of the last quantifiable concentration. |
| AUC_{∞} | Area under the plasma concentration-time curve from time 0 to infinity, calculated using the observed value of the last quantifiable concentration. |
| CCI | |
| | |
| | |
| | |
| | |
| C _{av,ss} | Average plasma concentration during a dosing interval, at steady state. |
| C _{av,ss} C _{max} | Average plasma concentration during a dosing interval, at steady state. Maximum observed plasma concentration. |
| C _{av,ss} C _{max} C _{max,ss} | Average plasma concentration during a dosing interval, at steady state. Maximum observed plasma concentration. Maximum observed plasma concentration during a dosing interval, at steady state. |
| C _{av,ss} C _{max} C _{max,ss} CL/F | Average plasma concentration during a dosing interval, at steady state. Maximum observed plasma concentration. Maximum observed plasma concentration during a dosing interval, at steady state. Apparent clearance after extravascular administration, calculated using the observed value of the last quantifiable concentration (TAK-653 only). |
| $C_{av,ss}$ C_{max} $C_{max,ss}$ CL/F λ_z | Average plasma concentration during a dosing interval, at steady state. Maximum observed plasma concentration. Maximum observed plasma concentration during a dosing interval, at steady state. Apparent clearance after extravascular administration, calculated using the observed value of the last quantifiable concentration (TAK-653 only). Terminal disposition phase rate constant. |
| C _{av,ss} C _{max} C _{max,ss} CL/F λ _z | Average plasma concentration during a dosing interval, at steady state. Maximum observed plasma concentration. Maximum observed plasma concentration during a dosing interval, at steady state. Apparent clearance after extravascular administration, calculated using the observed value of the last quantifiable concentration (TAK-653 only). Terminal disposition phase rate constant. |
| C _{av,ss} C _{max} C _{max,ss} CL/F λ _z CL/F | Average plasma concentration during a dosing interval, at steady state. Maximum observed plasma concentration. Maximum observed plasma concentration during a dosing interval, at steady state. Apparent clearance after extravascular administration, calculated using the observed value of the last quantifiable concentration (TAK-653 only). Terminal disposition phase rate constant. Time of first occurrence of C_{max}. |
| Cav,ss Cmax Cmax,ss CL/F λ _z c, t _{max} | Average plasma concentration during a dosing interval, at steady state. Maximum observed plasma concentration. Maximum observed plasma concentration during a dosing interval, at steady state. Apparent clearance after extravascular administration, calculated using the observed value of the last quantifiable concentration (TAK-653 only). Terminal disposition phase rate constant. |

Dose-normalized AUC, C_{max} , and $C_{max,ss}$ will also be calculated. Additional information regarding the plasma PK analysis and plasma PK parameter calculation and presentation will be provided in the Clinical Pharmacology Analysis Plan (CPAP). Additional plasma PK parameters may be calculated if necessary, in accordance with the CPAP.

Descriptive statistics (N, arithmetic mean, SD, median, minimum, maximum and %CV) will be used to summarize the plasma PK parameters for TAK653, ^{CCI} by TAK-653 dose level, Day, and period (fasted vs fed) for each part. In addition, geometric mean

| TAK-653-1001 | Page 21 of 32 |
|---------------------------------|----------------|
| Statistical Analysis Plan Final | 22 August 2017 |

and %CV will be computed for C_{max} and AUCs. Individual plasma PK parameters will be presented in a data listing for each part.

For each part, scatter plots of individual plasma TAK-653 ln-transformed Cmax and AUCs versus ln-transformed dose will be provided (fasted cohorts only).

Additionally, box plots of TAK-653 dose-normalized C_{max} and AUCs versus dose will be provided for each part (fasted cohorts only). Box plots of TAK-653 C_{max} and AUCs comparing fasted versus fed cohorts will also be provided.

Dose proportionality will be tested for SRD cohorts (fasted cohorts only) on Day 1 and for SRD/MRD cohorts after multiple dosing on Day 18 for TAK-653 C_{max} and AUCs using a power model. The power fit will be assumed as described by the following equation:

 $\ln(PK \ Parameter) = \beta_0 + \beta_1 \ln(Dose) + \varepsilon$

where β_0 is the intercept and β_1 is the slope. The dose proportionality will be declared when the 90% confidence interval for β_1 lies entirely within the critical region.

$$\left(1 + \frac{\ln(0.80)}{\ln(r)}, 1 + \frac{\ln(1.25)}{\ln(r)}\right)$$

where r is the ratio of the highest and the lowest dose in this study. This criterion implies that the 90% CI for the ratio of the central values of PK parameter of interest from the highest dose to the lowest dose is contained completely within the bioequivalence range of (0.80, 1.25) [2]. Plots of ln(AUC) or ln(C_{max}) vs ln(Dose) may also be used to illustrate dose proportionality or lack of it.

A power model will be performed to test whether the slope=1 in the power model and whether the point estimate of the slope is significantly different from 0 or not.

The effect of food on the PK of TAK-653 will be evaluated via a paired t-test. The point estimates and 90% CIs for the ratio of C_{max} and AUC central values for TAK-653 tablets administered after fed conditions vs those obtained in the fasted state will be determined. The food effect on t_{max} will also be evaluated using a non-parametric Wilcoxon rank sum test.

All attempts will be made to have a distribution of ^{CCI} times within the prescribed window of 2 to 6 hours postdose on Day 12 for SRD/MRD Cohort 3; for example, the ^{CCI} may be collected at 2 hours postdose from the first subject, 3 hours postdose from the

| TAK-653-1001 | Page 22 of 32 |
|---------------------------------|----------------|
| Statistical Analysis Plan Final | 22 August 2017 |
| | |

second subject, 4 hours postdose from the third subject, and 6 hours postdose from the fourth subject with a collection window of +1 hour for each subject.

| The CCI | , if available, will be presented |
|--|---------------------------------------|
| in a data listing. The ratio of TAK-653 ^{COI} | on Day 12 to the TAK-653 plasma |
| concentration on Day 12 will also be listed. TAK-653, ^{COI} | |
| | · · · · · · · · · · · · · · · · · · · |

and TAK-653^{CCI} plasma ratios will be summarized using descriptive statistics (N, arithmetic mean, SD, median, minimum, and maximum).

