4.3 Exploratory/ Additional Objectives

4.4 Study Design

This first-in-human, double-blind, placebo-controlled, combined single-rising dose (SRD)/multiple-rising dose (MRD) phase 1 study in healthy subjects is designed to assess the safety, tolerability, and PK of TAK-653. Approximately 112 healthy male and female volunteers will be enrolled.

This study consists of 2 parts: (1) single ascending doses in 5 cohorts (SRD) and (2) single and multiple ascending doses in 4 cohorts (SRD/MRD). Each cohort will consist of 8 subjects (6 active:2 placebo). Subjects will fast for at least 10 hours before dosing. Cohorts may be added or removed. The decision to dose will be based on emerging safety, PK, and PD data.

Follow-up assessments will occur approximately 14 days after the last dose of study drug to inquire about any ongoing adverse events (AEs) or serious adverse events (SAEs), worsening of AEs or SAEs, or development of new AEs or SAEs, and concomitant medications taken since

| TAK-653-1001 | Page 8 of 32 |
|---------------------------------|----------------|
| Statistical Analysis Plan Final | 22 August 2017 |

final dose. Follow-up will occur by telephone unless abnormal, clinically significant findings are observed upon discharge or at the investigator's discretion. Subjects should then be brought back to the clinic for re-evaluation.

| CCI | | |
|-----|--|--|
| | | |
| | | |
| | | |
| | | |

End of trial (study completion date) will be based on the final data collection date for the entire study which is the Follow-up call/visit.

Part 1: SRD

Subjects will be enrolled in SRD Cohorts. Sentinel dosing will be used for each SRD Cohort. The first 2 subjects (1 active: 1 placebo) in each Cohort will receive either TAK-653 or placebo in parallel, followed by a minimum 24-hour gap to ensure adequate evaluation of safety and tolerability prior to administering the same dose of TAK-653 or placebo to the remaining subjects within the Cohort (5 active: 1 placebo). Dosing of the remaining subjects will proceed in a staggered fashion with no more than 3 subjects being dosed at a time and having an approximate 24-hour gap before the next group of subjects is dosed. Each dose cohort will be examined sequentially to ensure adequate evaluation of all available safety, tolerability, PK, and PD data prior to administering the next dose level.

| Pretreatment Period | | Treatment Period | | | | Follow up (d) |

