(b) Dose escalation to Cohort 2 onward will be based on review of safety, tolerability, and available PK and PD data from the previous cohort(s).

(c) TAK-653 or placebo will be administered orally to subjects after an overnight fast of approximately 10 hours.(d) Subjects from SRD Cohort 3 (fasted conditions) will return to receive the same dose of TAK-653 following a standard meal.

Subjects in the SRD Cohorts will be kept in the study unit for approximately 96 hours after dosing for safety and PK assessments before discharge. The total confinement period is 5 days. Subjects in Cohorts 1 to 5 will return to the clinic on Days 6 and 7 for additional PK collections. Subjects in Cohort 6 onward will return to the clinic on Days 6, 7, and 8 for additional PK collections. If the $t_{1/2z}$ of TAK-653 for any cohort differs significantly from what was predicted, the duration of confinement may also be adjusted. Subjects in the food effect cohort will be confined twice for 5 days each for a total of 10 days. For SRD Cohort 6 onward,

ollow-up assessments for all subjects

in the SRD study arm will occur on Day 14 (± 2) .

Part 2: SRD/MRD

Progression into the SRD/MRD Part 2 will occur only after review of all available safety, tolerability, PK, and PD data collected in at least the first 3 SRD cohorts. The actual dose in the SRD/MRD Cohorts will not be administered unless there is acceptable safety, tolerability, PK, and PD data at the same or higher dose level after a single dose in the SRD Cohorts. If necessary, the sponsor team (Takeda only) may unblind the data and perform additional analyses for an informed dose-escalation decision. The potential for accumulation, and its

| TAK-653-1001 | Page 10 of 32 |
|---------------------------------|----------------|
| Statistical Analysis Plan Final | 22 August 2017 |

impact on the likelihood of reaching the no-observed-adverse-effect level exposure cap, will be taken into account when selecting doses for the MRD.

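### The SAP names an independent-samples test (Wilcoxon rank sum) for the food effect on tmax, although fasted and fed values come from the same subjects, at most six of them

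*SAP*

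**What the plan says.** The study design section of the SAP (4.4, note (d) to the Part 1 cohort table) sets up the food comparison: "Subjects from SRD Cohort 3 (fasted conditions) will return to receive the same dose of TAK-653 following a standard meal". Protocol 6.2.1 describes it as a comparison in which subjects act as their own controls.

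SAP 7.7.2 then gives the analysis. It opens with "The effect of food on the PK of TAK-653 will be evaluated via a paired t-test", asks for point estimates and 90% confidence intervals for the fed/fasted ratios of Cmax and AUC, and ends by saying that the food effect on tmax "will also be evaluated using a non-parametric Wilcoxon rank sum test".

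The protocol (Study Summary, Pharmacokinetic Measures) specifies the paired t-test for the logarithms of AUCs and Cmax and names no test for tmax. The rank sum test therefore appears only in the SAP, and SAP 7.11, on changes, does not mention it.

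**The concern.** The rank sum test treats its two samples as unrelated. Here each fed value has a fasted partner from the same person, so the test would handle up to six pairs as twelve independent values.

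Two things follow. The significance level actually achieved is unknown, because it moves with a within-subject correlation that the documents do not report. And the test ignores the direction of each subject's own change, which is what a crossover-type food comparison is meant to show. The SAP is also inconsistent with itself, since the same paragraph recognises the pairing.

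The opening t-test sentence names no parameter, so the word *also* could mean that the rank sum test supplements a paired t-test on tmax. On that reading too, the non-parametric test named is the wrong one for paired data.

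**Working it through.** **How many pairs.** SAP 4.4: "Each cohort will consist of 8 subjects (6 active:2 placebo"). SAP 7.7.1: "Blood samples for placebo will not be analyzed by the bioanalytical laboratory except for 2 samples per subject receiving placebo". Placebo subjects therefore have no tmax profile, and Cohort 3 gives at most 6 fasted-fed pairs. SAP 7.1 sets two-sided tests at 0.05. The plan states no figure for this comparison, so there is none to reproduce.

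**What each test can attain with 6 pairs.**
- Rank sum: C(12,6) = 924 allocations. Smallest two-sided p = 2/924 = 0.002; largest attainable level not above 0.05 is 0.041.
- Signed-rank: 2^6 = 64 sign patterns. Smallest two-sided p = 2/64 = 0.031, reached only if all six differences have the same sign. With 5 pairs it is 2/32 = 0.0625.

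**Illustration (assumed data on the SAP sampling grid).** Every subject peaks one scheduled sample later when fed.
- Fasted: 1, 1.5, 2, 3, 4, 6 h. Fed: 1.5, 2, 3, 4, 6, 8 h.
- Rank sum with midranks: fed ranks 2.5 + 4.5 + 6.5 + 8.5 + 10.5 + 12 = 44.5, against 39 expected. 420 of the 924 allocations are at least as extreme: p = 420/924 = 0.45.
- The SAP does not use scheduled times: "Actual sampling times, rather than scheduled sampling times, will be used in all computations involving sampling times". Minutes would then break the five cross-period ties. Over all 32 ways of breaking them by one minute, p runs from 222/924 = 0.24 to 646/924 = 0.70.
- Signed-rank: differences 0.5, 0.5, 1, 1, 2, 2 h, all positive, so p = 2/64 = 0.031 in every case.

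**True type I error at two-sided 0.05.** Simulated with 6 pairs, no food effect, no ties and lognormal tmax with log-scale correlation rho. The rho values are assumptions. With no ties these error rates do not depend on the assumed median or spread.

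| rho | rank sum | signed-rank |
|---|---|---|
| -0.3 | 0.068 | 0.031 |
| -0.1 | 0.049 | 0.031 |
| 0 | 0.041 | 0.031 |
| 0.3 | 0.021 | 0.031 |
| 0.5 | 0.010 | 0.031 |
| 0.7 | 0.004 | 0.031 |

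The rank-sum rate falls below its attainable 0.041 for any positive correlation and rises above it for any negative one. It passes 0.05 only when rho is below about -0.1. With actual draw times inside the windows of protocol Table 14.a (assumed median tmax 3 h, log-SD 0.5), the pattern is the same: rank sum 0.065 at rho = -0.3 down to 0.006 at 0.7, signed-rank 0.030 to 0.034.

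**The case against.** The strongest reply is that this matters little and may be a slip of the pen. The authors plainly knew that the data were paired. The food assessment is called preliminary (protocol 6.1), "The sample size was not based on statistical power considerations", and no decision depends on this test. Individual tmax values are listed, so a reader can see each pair. Detail is also deferred: "Additional information regarding the plasma PK analysis and plasma PK parameter calculation and presentation will be provided in the Clinical Pharmacology Analysis Plan (CPAP"). That plan is not among the documents and may already name a paired test. All of this stands, and it limits the finding to the SAP wording and to minor impact.

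A second reply is that the signed-rank test is not clearly better with six pairs. That is also fair:
- For a 1.5-fold delay on actual times (same assumed median and spread), power for rank sum against signed-rank is 0.20 v 0.13 at rho 0, 0.17 v 0.17 at 0.3, 0.16 v 0.21 at 0.5 and 0.14 v 0.31 at 0.7.
- If one subject does not return, the signed-rank test cannot reach 0.05.
- If scheduled times were used and same-sample pairs dropped, which is not the SAP rule, the signed-rank test would be the more conservative of the two for rho up to 0.5.
- Under the actual-time rule, a subject who peaks at the same scheduled sample in both periods gets a sign from a few minutes' difference in draw time.
- The illustration above is the pattern most favourable to the signed-rank test.

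These points rule out power as the argument. They do not make an independent-samples test valid for paired data. Positive correlation would make the rank sum test conservative rather than prone to false food effects, but its actual level would still be unknown.

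**Conclusion.** The concern holds. As written, SAP 7.7.2 assigns an independent-samples test to data that are paired by design, against its own treatment of the food effect in the same paragraph. The size of the error depends on an unreported correlation: over the assumed range from -0.3 to 0.7, the true level of a nominal 0.05 test runs from about 0.068 down to 0.004, while a signed-rank test holds at 0.031. The case rests on validity and consistency with the design, not on gain in power. The consequence is minor and confined to the tmax food comparison. The conclusion concerns the SAP text; what was finally run cannot be judged without the Clinical Pharmacology Analysis Plan.

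**What to change.** In SAP 7.7.2, replace the rank sum test with: *Wilcoxon signed-rank test on within-subject (fed minus fasted) differences in tmax, in TAK-653 subjects with tmax in both periods.* If the Clinical Pharmacology Analysis Plan already specifies a paired test for tmax, align the SAP sentence with it.

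A useful addition, because the test is so coarse at this size, is the Hodges-Lehmann estimate of the paired shift with its exact confidence interval nearest 90%. The attainable level is 1 - 2 × 3/64 = 90.6% with 6 pairs and 1 - 2 × 2/32 = 87.5% with 5. In the illustration the estimate is 1.25 h (the median of the 21 Walsh averages), with 90.6% interval 0.5 to 2.0 h. It should be labelled as such, since the plain median difference there is 1.0 h. A short statement of how pairs peaking at the same scheduled sample are handled would also help.

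The cost is one SAP sentence and one procedure call, with no new data. The price of the correct test is its floor: p cannot go below 0.031 with 6 non-zero pairs, or 0.0625 with 5.
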